4.2.3. Sensitivity analyses

Sensitivity Analyses
Sensitivity Analysis for assumptions regarding missing data

 Missing Data Imputation:

The negative binomial model assumes missing data is missing at random. To assess the robustness of the primary estimand to departures from this assumption, a sensitivity analysis in the mITT population will be performed where missing data will be imputed.

Participants who withdrew from the study early will have missing data imputed for the period of time between withdrawal from the study and their scheduled end of study. Missing data for these subjects will be imputed using observed off-treatment data collected from randomized participants (prior to occurrence of intercurrent events of IP discontinuation or interruption of 2 or more consecutive doses of IP associated with the COVID-19 pandemic) who continued in the study following discontinuation of randomized treatment.

Participants who have missing data due to occurrence of intercurrent events of IP discontinuation or interruption of 2 or more consecutive doses of IP associated with the COVID-19 pandemic will have missing data imputed for the period of time between occurrence of the intercurrent event and their scheduled end of study. Missing data after the occurrence of the intercurrent event will be imputed using both on-treatment and off-treatment data collected from randomized participants (on-treatment data prior to occurrence of intercurrent events associated with the COVID-19 pandemic, off treatment data from those not experiencing an occurrence of intercurrent events associated with the COVID-19 pandemic).

Missing data is imputed multiple times for each subject based on a combination of their respective covariates and the observed data. The imputed data is combined with the observed exacerbations and the data is analyzed as for the primary endpoint. This analysis is repeated multiple times and the results combined across imputations using Rubin's formulae [Rubin, 1987] as implemented in PROC MIANALYZE in SAS.

- Tipping Point:

A tipping point sensitivity analysis will be performed for the primary endpoint of annualized rate of moderate/severe exacerbations in the mITT population. This will explore the impact of missing data by using differing assumptions regarding the exacerbation rate in participants with missing data. Participants who withdrew from the study or experienced intercurrent events of IP discontinuation or interruption of 2 or more consecutive doses of IP associated with the COVID-19 pandemic will have missing data imputed for the period of time from study withdrawal/occurrence of event to their scheduled end of study. The missing data will be imputed based on a range of increases in exacerbation rates relative to the estimated rates obtained within each arm under the MAR assumption. The imputed exacerbation rates will vary independently for the mepolizumab and placebo arms and will include scenarios where participants with missing data in the mepolizumab arm have worse outcomes than participants in the placebo arm. As before, multiple imputation methods will be used, and results will be combined across imputations using Rubin's method. The analysis results will be used to explore conditions under which there is no evidence of a treatment effect and clinical judgment will be applied as to the plausibility of the associated assumptions.

- Site 239718:

A sensitivity analysis will be conducted excluding the three subjects randomized at Site 239718. This will explore the impact of patients from this site on the primary estimand. The analysis will otherwise be carried out as outlined within Section 4.2.2.

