4.1.4. Study Completion

The study is designed to collect data after premature discontinuation of treatment. Participants are considered to have completed the study if they meet the following criteria regardless of premature discontinuation of interventional product.

Participants enrolled for 52 Weeks

A participant is considered to have completed the study if they continue to participate in the study until the Exit Visit at Week 52.

Participants enrolled beyond 52 Weeks (or re consented to continue beyond 52 Weeks)

A participant is considered to have completed the study if they continue to participate in the study until the earlier of:

The Exit Visit at Week 104

OR

A scheduled visit that is on or immediately before the date of the Exit Visit at Week 52 of the last participant to have been randomized into the study.

By study design, the duration of study will vary for the participants enrolled beyond 52 Weeks (or re consented to continue beyond 52 Weeks).

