4.2. Primary Endpoint Analyses

4.2.1. Definition of Primary Endpoint/Estimand

The primary endpoint is the annualized rate of moderate or severe exacerbations occurring during the study period. The study is designed to continue collecting exacerbation data for participants who have prematurely discontinued from IP and remain in the study.

For analysis, moderate exacerbations are defined as clinically significant exacerbations that require treatment with oral/systemic corticosteroids and/or antibiotics. Severe exacerbations are defined per protocol as clinically significant exacerbations that require in-patient hospitalization (i.e., ≥ 24 hrs.) or result in death. The study inclusion criteria required at least 2 moderate COPD exacerbations treated with systemic corticosteroids (intramuscular (IM), intravenous, or oral) with or without antibiotics or at least one severe exacerbation in the 12 months prior to Screening Visit 1.

Moderate and severe exacerbations occurring from the start of interventional product (IP) will be included in the primary analysis regardless of whether the exacerbation occurs after a participant prematurely discontinues from IP. For participants who complete the study (Section 4.1.4), all moderate/severe exacerbations occurring up to study completion will be included in the primary analysis. For participants who withdraw early from the study all moderate/severe exacerbations occurring up to the date of study withdrawal will be included in the primary analysis, these participants will be considered to have missing data from the date of study withdrawal up to their planned study completion date.

For all summaries and analyses, exacerbations occurring within 7 days of each other within a given participant will be handled as a continuation of the same exacerbation, assigned to the greatest severity.

The primary estimand is the difference between mepolizumab 100 mg SC and placebo (both added to optimized standard of care) in the annualized rate of moderate/severe exacerbations in participants with COPD experiencing frequent exacerbations and characterized by eosinophil levels, regardless of IP discontinuation/interruption or changes in background medication/starting a prohibited medication, in the absence of COVID-19 pandemic related intercurrent events.

The primary estimand is described by the following attributes:

Population: Participants with COPD experiencing frequent exacerbations and characterized by eosinophil levels

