Treatment condition: Mepolizumab 100 mg SC vs. placebo (both as add-on treatment to optimized standard of care)

Variable: Number of moderate or severe exacerbations

Summary Measure: The summary measure of treatment effect will be the ratio of the frequency of exacerbations in the mepolizumab 100 mg treatment arm to the frequency in the placebo arm. Exacerbation rates will be expressed as an annualized exacerbation rate.

Intercurrent events: The anticipated intercurrent events for this trial are discontinuation of IP, interruption of 2 or more consecutive doses of IP, use of prohibited medications and change in background medication.

A treatment policy strategy will be used to handle the intercurrent events of discontinuation of IP and interruption of 2 or more consecutive doses of IP when not associated with disruptions or restrictions (e.g. lockdown measures, social distancing) imposed due to the COVID-19 pandemic, under this strategy exacerbations and time in study will be included in the analysis regardless of the intercurrent event. A hypothetical strategy will be used to handle these intercurrent events when they are known to be associated with disruptions or restrictions imposed due to the COVID-19 pandemic. Under this strategy exacerbations, and the period of time in study occurring after the intercurrent event, will be set to missing and handled as missing data.

A treatment policy strategy will be used to handle the intercurrent events of change in background therapy and use of prohibited medications.

Rationale for estimand: The use of a hypothetical strategy recognizes any effect on exacerbations due to discontinuation /interruption of 2 or more consecutive doses of IP associated with disruptions or restrictions imposed due to the COVID-19 pandemic, may not have occurred in the hypothetical scenario of the absence of the pandemic.

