6.2.2. Study Period

6.2.2.1. Analysis Period

The analysis period for exacerbations and efficacy endpoints is defined as the period of time over which exacerbations and efficacy assessments will be included in the on- and/or off-treatment phases (See Section 6.2.3.1). The start and end of the analysis period is defined as follows:

Analysis Period for Exacerbations and Efficacy Endpoints		
Study Completion	Start Date of Analysis Period	End Date of Analysis Period ^[1]
Participants enrolled for 52 weeks		
Completed	First dose of interventional product (Day 1)	Earlier of Date of Week 52 Exit Visit or Day 372
Withdrew Early	First dose of interventional product (Day 1)	Earlier of Date reported on the study conclusion page ^[2] or Day 372
Participants consented to participate for more than 52 weeks		
Completed	First dose of interventional product (Day 1)	Earlier of Date of Week 104 Exit visit or Day 736 or scheduled visit on or immediately before the date of Week 52 Exit Visit of the last participant to have been randomized into the study
Withdrew Early	First dose of interventional product (Day 1)	Earlier of Date reported on the study conclusion page or Day 736

[1] Allowing for the ±7 day visit window in the protocol; Day 372/736 is defined as 371/735 days (364+7 days / 728+7 days) after the first dose of interventional product.

[2] eCRF completion guidelines state ‘COPD exacerbation details are collected from Screening Visit 1 through to last follow up (study conclusion date)’

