6.2.2.2. Length of Time in Phase

The length of time in a phase reflects for each participant the period of time over which exacerbation data has been recorded and included in the negative binomial analysis model. The analysis model will incorporate this information as an offset of \log_e (length of time (years) in phase).

Length of time (years) will be calculated as Length of time (Days)/365.25.

The length of time a participant contributes information in each phase is detailed below. For participants who completed the study and did not withdraw early from interventional product, the on-treatment period is the full analysis period; these participants have no off-treatment data. For participants who withdrew early from interventional product the on-treatment and off-treatment periods are as described in the table below:

Exacerbations – Length of Time in Phase	
Phase	Length of time (Days) in Phase
On- and Off-treatment	(Date of End of Analysis Period – IP Start Date) +1
On-treatment	If End of Analysis Period ≤28 days after last dose: (Date of End of Analysis Period – IP Start Date) +1 If End of Analysis Period >28 days after last dose: (IP Stop Date – IP Start Date) +29
Off-treatment	If End of Analysis Period ≤28 days after last dose: 0 days If End of Analysis Period >28 days after last dose: Date of End of Analysis Period – [IP Stop Date + 28 days]

Participants who withdrew early from the study with an analysis period which ends prior to their planned study completion date (see Section 4.1.4), will be considered to have missing data for the period of time from the end of the analysis period to their planned study completion date.

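### Does the SAP need a written rule that stops imputation of exacerbations at death?

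*SAP*

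**What the plan says.** SAP 4.2.1 names the events that the primary estimand must handle: "The anticipated intercurrent events for this trial are discontinuation of IP, interruption of 2 or more consecutive doses of IP, use of prohibited medications and" a change in background treatment. Death is not listed. It enters the primary endpoint only through the severity definition (SAP 4.2.1, Protocol 8.1.1), under which a fatal exacerbation counts as one severe event.

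For participants who leave early, SAP 4.2.1 says "these participants will be considered to have missing data from the date of study withdrawal up to their planned study completion date". SAP 6.2.2.2 repeats this for "Participants who withdrew early from the study with an analysis period which ends prior to their planned study completion date". A participant enrolled for 52 weeks completes if "they continue to participate in the study until the Exit Visit at Week 52" (SAP 4.1.4). The table in SAP 6.2.2.1 has only two states, completed and withdrew early. For early leavers in the extended group the analysis period ends at "Earlier of Date reported on the study conclusion page or Day 736".

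Two sensitivity analyses in SAP 4.2.3 fill the missing window. The off-treatment imputation says "Participants who withdrew from the study early will have missing data imputed for the period of time between withdrawal from the study" and the scheduled end of study. In the tipping-point analysis, the same participants, and those with COVID-associated events, "will have missing data imputed for the period of time from study withdrawal/occurrence of event to their scheduled end of study". Its result is then interpreted: "clinical judgment will be applied as to the plausibility of the associated assumptions". Neither analysis mentions death.

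**The concern.** A participant who dies before the Exit Visit has not completed. With only two states available, death seems to fall under early withdrawal. The time up to the planned completion date would then be missing, and both analyses would generate exacerbations for a person who can have none.

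These are the stated robustness checks on the primary endpoint. The tipping-point result is a multiplier on the exacerbation rate, judged for clinical plausibility. If part of the imputed time follows death, a smaller multiplier on the mepolizumab arm is enough to remove significance, and a clinician cannot easily judge a rate assigned to people who have died.

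**Working it through.** **What the text supports.** Protocol 7.2 describes withdrawal as the participant's request or the investigator's decision, and 7.3 adds loss to follow-up. Neither names death. On that wording a death need not trigger imputation; on the two-state table it would. The text supports only that the handling is unspecified.

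**The plan's own figure.** Inputs from SAP 5: placebo rate 1.7, ratio 0.77, dispersion 0.55, 90% power, two-sided 5%, one year of follow-up.

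- n per arm = (1.960 + 1.282)² × [1/1.7 + 1/(1.7 × 0.77) + 2 × 0.55] / (ln 0.77)² = 377.2, rounded up to 378.
- Total 756; 756/(1 − 0.055) = 800, as stated.
- The smallest significant reduction comes out at 14.4–14.6%, against the stated 15%.

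**Post-death time.** The documents give no mortality rate, so m = 1%, 2% or 4% per year in both arms is assumed. Suppose the 5.5% of missing patient-years (SAP 5) includes deaths. The total exit hazard h solves 1 − (1 − e^(−h))/h = 0.055, so h = 0.1142 per year. Deaths open a share m/h of the missing time, and p = 0.055 × m/h is the post-death share of planned time at 52 weeks.

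| m | m/h | p | mepolizumab post-death time at placebo rate: 0.77(1 − p) + p | its mepolizumab rate doubled: 0.77(1 + p) | placebo rate doubled instead: 0.77/(1 + p) |
|---|---|---|---|---|---|
| 1% | 8.8% | 0.48% | 0.771 | 0.774 | 0.766 |
| 2% | 17.5% | 0.96% | 0.772 | 0.777 | 0.763 |
| 4% | 35.0% | 1.93% | 0.774 | 0.785 | 0.755 |

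The last column matters because SAP 4.2.3 varies the two arms independently. The direction depends on which arm's rate is raised, and on mortality by arm.

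At an assumed 1.5 years of follow-up and m = 2–4%, p is 1.4–2.8%. Doubling the mepolizumab rate then gives at most 0.77 × 1.0284 = 0.792. A harsher case, 5% yearly mortality with all participants followed for 104 weeks and no other losses, gives p = 5.0% and 0.77 × 1.0496 = 0.808.

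**Tipping multiplier.** The multiplier on the mepolizumab rate that takes 0.77 to 0.85 is 1 + (0.85/0.77 − 1)/s, where s is the imputed share of planned time.

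- With only the 5.5% imputed: s = 0.055 gives 2.9. Ending imputation at death (m = 2–4%) leaves s = 0.0454–0.0357 and gives 3.3–3.9. At m = 1% it is 3.1.
- SAP 4.2.3 also imputes time after COVID-associated stopping or interruption of study drug, which the 5.5% from a pre-pandemic study does not cover. An assumed extra 1% of person-years gives 2.6, against 2.9–3.3 with imputation ended at death. An extra 3% gives 2.2, against 2.4–2.6.
- If the 5.5% excludes deaths and there is no COVID time, the values are 2.4–2.6 against 2.9.

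**A borderline result.** From an observed 0.85 with p = 1.93% at the placebo rate, the ratio is 0.85 × 0.9807 + 0.0193 = 0.853, still below the computed critical value of 0.856. It would cross at about 5% of person-time: 0.85 × 0.95 + 0.05 = 0.8575.

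**The case for a change.** The best case for a change is that both readings leave a hole. Either death counts as withdrawal and post-death time is imputed, or a participant who dies fits neither row of the analysis-period table. What counts as missing data in the checks on a primary estimand belongs in the SAP rather than in programming notes. The cost would be one or two sentences. A death form is already required (Protocol 8.3.6), and all-cause mortality is already an endpoint (SAP 1.1.1). The multiplier also moves more than the rate ratio does.

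The gap itself stands. The step from there to a needed correction does not, for three reasons.

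- Ending imputation at death is not neutral. It adopts a while-alive reading, on which statisticians differ, and rules out a hypothetical strategy that the sponsor might prefer.
- It has a cost: the sensitivity analyses would no longer probe informative loss through death. It would also be incomplete, because Protocol 8.3.1 does not require investigators to look for deaths after a participant has left.
- The multiplier contrast is largest when COVID-associated imputed time is left out, and it narrows once that time is counted.

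**Conclusion.** No change follows. This is missing detail that analysts can settle before unblinding, joined to a fair trade-off over how to treat death. The primary negative binomial analysis imputes nothing and uses observed time as its offset, so its result stands, as do the testing hierarchy and N = 800. Fatal exacerbations are already counted, and deaths are reported separately as a safety endpoint, so the tipping-point result can be read beside them.

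At an assumed 1–4% yearly mortality, equal in both arms, post-death time at 52 weeks is about 0.5–1.9% of planned person-years. It moves a ratio of 0.77 to somewhere between 0.755 and 0.785, depending on which arm's rate is raised. The highest value is 0.792 at 1.5 years, and 0.808 in the harsher 104-week case, against a limit of about 0.85. That limit applies to 800 participants followed for 52 weeks; the design allows up to 1400 participants and 104 weeks. The handling of death would matter only for a borderline primary result, unusually high mortality or a strong tipping scenario. Whether post-death time is imputed at all remains an inference, since the study conclusion page and the Output and Programming Specification cited in SAP 6.1.4 are not available.

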4.2.4. Additional estimands

Additional Estimands

Additional (supplementary) estimands for the primary endpoint will be presented for the mITT population whereby a treatment policy strategy will be used for all intercurrent events whether or not associated to the COVID-19 pandemic.

Analysis will be as for the primary estimand and missing data due to study withdrawal will be handled as missing at random. In a separate analysis missing data will be imputed using observed off-treatment data collected from randomized participants who continued in the study following discontinuation of randomized treatment.

These additional estimands estimate the difference between mepolizumab 100 mg SC and placebo (both added to optimized standard of care) in the annualized rate of moderate/severe exacerbations in participants with COPD experiencing frequent exacerbations and characterized by eosinophil levels, regardless of IP discontinuation/interruption, changes in background medication/starting a prohibited medication, or the impact of the COVID-19 pandemic.

4.2.5. Exploratory Modelling

The role of blood eosinophil counts on the effectiveness of mepolizumab with respect to the number of moderate/severe exacerbations will be investigated. The number of moderate/severe exacerbations will be predicted at each level of the screening \log_e blood eosinophil count based on a model including a screening \log_e blood eosinophil count main effect term and an interaction with treatment term.

The best fitting form of the interaction (i.e. which maximizes the likelihood function) between treatment group and screening \log_e blood eosinophil count will also be explored.

4.3. Secondary Endpoint(s) Analyses

For all secondary endpoints the primary population of interest, the treatment condition, and handling of intercurrent events will be as described for the primary estimand (Section 4.2.1). Unless otherwise specified all analyses will include data regardless of discontinuation of interventional product as has been detailed for the primary endpoint.

4.3.1. Time to first moderate/severe exacerbation

4.3.1.1. Definition of Endpoint

The time to first moderate/severe exacerbation will be determined as the number of days from the date of first dose to the date of the first moderate or severe exacerbation:

Time to first exacerbation = date of first exacerbation – date of first dose +1

Partial dates related to exacerbations will be queried, in the event the full start date cannot be determined, imputation as described in Section 6.2.7 will be applied.

The variable of interest is the time to first moderate/severe exacerbation. Participants who complete the study without experiencing a moderate/severe exacerbation will be censored at their scheduled end of the study treatment period (see Section 6.2.2.1). Participants who withdrew early from the study or experienced an intercurrent event of IP discontinuation or interruption of 2 or more consecutive doses of IP associated with the COVID-19 pandemic before experiencing an exacerbation will be censored at the earliest of the date of study withdrawal and the start date of COVID-19 pandemic associated intercurrent event of IP discontinuation or interruption of 2 or more consecutive doses of IP.

The summary measure of treatment effect will be the hazard ratio, the ratio of hazards corresponding to treatment with mepolizumab compared with placebo. For this endpoint the hazard represents the probability of moderate/severe exacerbation for a participant at a given point in time following first dose of interventional product, given the participant has not experienced the event prior to that time. Data will be presented up to week 104 for this endpoint.

4.3.1.2. Main Analytical Approach

Statistical Methodology Specification

Endpoint / Variables					
Time to first moderate/severe exacerbation (mITT and mITT2)					
Model Specification					

 Analysis of time to first moderate/severe exacerbation will use a Cox proportional hazards model with covariates as shown. Missing values will be considered as censored at random (non-informative censoring). 
 
 Fixed Categorical:	Treatment group, smoking status, geographic region	
 
 Fixed Continuous:	Baseline disease severity (as % predicted post-bronchodilator FEV₁), number of moderate/severe exacerbations in previous year (≤2, 3, ≥4 as ordinal)	
 
 
 Participants with missing covariate information will be excluded from the analysis. 		Fixed Categorical:	Treatment group, smoking status, geographic region	Fixed Continuous:	Baseline disease severity (as % predicted post-bronchodilator FEV ₁), number of moderate/severe exacerbations in previous year (≤2, 3, ≥4 as ordinal)
Fixed Categorical:	Treatment group, smoking status, geographic region				
Fixed Continuous:	Baseline disease severity (as % predicted post-bronchodilator FEV ₁), number of moderate/severe exacerbations in previous year (≤2, 3, ≥4 as ordinal)				
Model Checking & Diagnostics					
A log(-log(survival)) plot by treatment group will be used to assess the assumption of proportional hazards.					
Model Results Presentation					

 The number of participants with an event, the number censored due to study withdrawal, due to an intercurrent event associated to the COVID-19 pandemic, and at study completion will be presented by treatment arm. The hazard ratio with corresponding 95% CI and p-value from the Cox proportional hazards model will be presented. 
A summary and graph of the Kaplan-Meier estimate of the cumulative proportion of participants with a moderate/severe exacerbation within each treatment arm over time will be produced.
					

Subgroup Analyses

Separate exploratory subgroup analyses will be carried out as outlined in Section 4.10.1.

